## **Placebo**

There is no matching placebo. The control group will not receive GTN, and matching placebo GTN patches are not available. Instead, a sham patch of similar size to the GTN patch (Duoderm – a hydrocolloid dressing of size 4.4cm x 3.8cm) will be used. Like the GTN patch, it will be placed on the shoulders or back and the position rotated daily. Duoderm patches are manufactured by Convatec and are presented in individually wrapped packages. They do not have identifying information on them. Sham-Duoderm patches will be covered by a gauze dressing to conceal treatment allocation.

## **Trial packaging**

The placebo packs will be manufactured, supplied, packaged, labelled and QP released to provide blinded treatment packs and distributed in the same way as the active IMP. Storage, dispensing and return of the sham patch will be the same as the active IMP.

## **Known side effects of placebo patches**

There is the possibility of allergic reactions to the product or its components. Patients who have a known sensitivity or allergy to the product or its components should therefore not participate in the study.

**Reference Safety Information:** Section 4.8 Transiderm Nitro SmPC

# **TRIAL / STUDY OBJECTIVES AND PURPOSE**

## **PURPOSE**

- The purpose of the study is to determine whether it is feasible to recruit patients and administer GTN within the 3-5-hour time window after the onset of stroke.

## **PRIMARY OBJECTIVE**

- To assess the feasibility of recruiting, randomising, and treating patients with GTN vs sham to inform a definitive trial.

## **SECONDARY OBJECTIVES**

- To determine signals of efficacy on whether GTN reduces disability, low mood, poor cognition, and low quality of life.
- To investigate whether there is a difference between the two groups in blood pressure measured over the two days of monitoring.

- To investigate whether specific genetic characteristics are associated with outcome. Potential genetic markers include nitric oxide synthase polymorphisms, but others will be studied as relevant in searches of the scientific literature.
- To investigate whether there is a difference in blood biomarkers between the two groups and whether biomarkers may be associated with outcome. Potential biomarkers include S-100 / nitric oxide (NOx) but others will be studied as relevant in searches of the scientific literature.

## **TRIAL / STUDY DESIGN**

### **TRIAL CONFIGURATION**

Prospective parallel-group randomised sham-controlled phase II feasibility and safety trial of GTN versus sham given initially between 3 and 5 hours after stroke, and then at 09.00 on the next day.

#### **Primary endpoint**

The primary end point of the study is the feasibility of recruiting and treating 120 patients (100 IS, 20 ICH) between 3 and 5 hours after stroke.

#### **Secondary endpoints**

Hospital admission:

- Neurological impairment (NIHSS)
- Systolic and diastolic blood pressure, heart rate.
- Proportion of participants with systolic blood pressure <185 mmHg.
- Feeding and dysphagia (dysphagia severity rating scale)
- Stroke lesion size on brain scan (non-contrast CT or T2 MR).
- Amount of cerebral arterial patency on brain scan (CT or MR angiography).

Hospital utilisation:

- Open-label blood pressure lowering.
- Intravenous thrombolysis.
- Mechanical thrombectomy.
- Hyperacute stroke unit.
- Stroke Rehabilitation Unit.
- Physiotherapy.
- Occupational therapy.
- Speech & language therapy.
- Surgery for IS - Hemicraniectomy.
- Surgery for ICH.
- Days in intensive/critical care unit.

At day 2:

- Systolic and diastolic blood pressure, heart rate.

#### At day 2: Biomarkers

- Blood biomarkers (exact measures to be determined by literature review prior to measurement but examples include S-100, NOx).
- Genetic markers (exact measures to be determined by literature review prior to measurement but examples include NO synthase polymorphisms).

#### At day 2 (or discharge if sooner):

- Neurological impairment (NIHSS).
- Stroke recurrence.
- Neurological deterioration from baseline (NIHSS  $\geq 4$  points, or  $\geq 2$ -point increase in any domain).
- Feeding and dysphagia (DSRS).

#### At discharge/death

- Length of stay in hospital
- Patient disposition.

#### At day 90 by telephone (or post):

- Dependency – modified Rankin Scale (primary endpoint at Day 90).
- Disability/Activities of Daily Living - Barthel Index (BI).
- Quality of life - Health Utility Status (HUS, derived from EuroQoL-5D), EQ-Visual Analogue Scale (EQ-VAS).
- Cognition - telephone-MMSE, Telephone Interview Cognition Scale (TICS), animal naming.
- Mood - Zung Depression Scale.
- Patient disposition (died, institution/in hospital, home).

### **Safety endpoints**

#### By day 2

- Any serious adverse event.
- Headache.
- Infection (pneumonia/chest, urinary tract, other).
- Hypotension requiring clinical intervention.
- Hypertension requiring clinical intervention.

#### From day 3 to day 90

- Any fatal serious adverse event.

Data on stroke recurrence and acute coronary syndrome, termed safety outcome events, will be collected up to day 90.

### **Stopping rules and discontinuation**

The DMC review unblind data twice yearly in respect of safety and efficacy and consider the study in the context of other trials of altering BP in stroke. Since the main aim of the study is to assess feasibility, the trial will not be discontinued unless the safety of participants is likely to be compromised. The DMC also monitor SAEs and neurological deterioration, and outcome in IS and ICH separately.

## **RANDOMISATION AND BLINDING**

All participants eligible for inclusion will be randomised centrally using a secure internet site in real-time. Randomisation will be 1:1 GTN: sham and involve computerised stratification by stroke type (ischaemic stroke or not known vs ICH) and minimisation on age, severity, time, systolic blood pressure and candidate for or received reperfusion therapy (alteplase, and/or mechanical thrombectomy). This approach ensures concealment of allocation, minimises differences in key baseline prognostic variables, and slightly improves statistical power (16). Patients, relatives, researchers, and outcome assessors will be masked to treatment allocation.

In order to minimise selection bias, a participant must be enrolled in the study before they are randomised on the internet site. Randomisation will allocate a number corresponding to a treatment pack and the participant will receive treatment from the allocated numbered pack.

In the event of computer failure (for example: server failure), investigators will follow the working practice document for computer system disaster recovery, which will allow the participant to be randomised following standardised operating procedure.

Personnel applying the GTN/sham patches will not be blinded to the treatment allocation as the sachets around the patches are different and carry the manufacturers identifying information.

### **Maintenance of randomisation codes and procedures for breaking code**

Although both the GTN and sham patches have no identifying information on them, they look slightly different, and it will be obvious to nurses when administering treatment. Since GTN and sham patches will be placed on the participant's shoulder or back, it will be difficult for them to recognise the treatment that they have received.

In order to minimise bias that could be introduced through knowledge of what the participant has received, unmasked staff will be kept to a minimum and be asked not to reveal the treatment to anyone. In addition, the primary end-point of the study will be recorded by personnel masked to treatment assignment.

### **Unblinding**

In the event of breaking the treatment code this will normally be recorded as part of managing a SAE (see below for more details) and such actions will be reported in a timely manner. The investigator may unblind themselves by removing the gauze from the patch. The GTN is identifiable by medical staff. The Chief Investigator (delegated the sponsor's responsibilities) shall be informed immediately (within 24 hours) of any serious adverse events and shall determine seriousness and causality in conjunction with any treating medical practitioners.

## **TRIAL MANAGEMENT**

Day-to-day management of the trial will be the responsibility of the Trial Management Committee (TMC). The TMC will report to the Trial Steering Committee (TSC). An independent Data Monitoring Committee (DMC) will monitor the safety of participants and will advise the TSC on safety. Trial co-ordination will pass through the Nottingham Stroke Trials Unit and members of the TMC.

The Chief Investigator has overall responsibility for the study and shall oversee all study management.

The data custodian will be the Chief Investigator.

### **Trial Management Committee (TMC)**

The Trial Management Committee will include the Trial Manager (who will chair meetings), Chief Investigator, Trial Coordinators, Trial Statistician, Trial Programmer, and other project staff. This group, based at the Nottingham Stroke Trials Unit, will meet at least monthly or as necessary.

### **Trial Steering Committee (TSC)**

The Trial Steering Committee will provide oversight of the trial. It will meet (in person or by telephone conference) prior to commencement of the trial, and then at regular intervals (at least annually) until completion. The TSC will be chaired by an independent member and comprise two other independent members, the Grant Applicants (including the lay member), and representatives of the sponsor and funder. The standard University of Nottingham Trial Steering Committee Charter and Contracts will be used.

Specific tasks of the TSC are:

- To approve the trial protocol.
- To approve necessary changes to the protocol based on considerations of feasibility and practicability.
- To receive and review reports from the DMC.
- To resolve problems brought to it by the co-ordinating centre and TMC.
- To lead on publication of the trial results.

### **Data Monitoring Committee (DMC)**

An independent Data Monitoring Committee will be established. The DMC will receive safety reports every six months, or more frequently if requested, and perform unmasked reviews of efficacy and safety data. No interim analysis will be performed.

The standard University of Nottingham Data Monitoring Committee Charter and Contracts will be used containing details of membership, terms and conditions and full details of stopping guidelines. The DMC will report their assessment to the independent chair of the TSC and the CI. They will not, however, provide specific unmasked results to the TSC or Chief Investigator.

## **DURATION OF THE TRIAL / STUDY AND PARTICIPANT INVOLVEMENT**

**Participant Duration:** The study will recruit patients for 31 months. The participant's involvement in the trial will last for 3 months, from randomisation (day 1) until final follow-up at 90 days. Treatment will last 2 days (enrolment day and next day).

**Study Duration:** The study will recruit patients for 31 months. The participant's involvement in the trial will last for 3 months, from randomisation (day 1) until final follow-up at 90 days.

Treatment will last 2 days (enrolment day and next day). Total study duration will be 36 months.

## **End of the Trial**

The end of the study will be the last treatment period and follow up (Day 90) of the last participant (LPLV).

## **SELECTION AND WITHDRAWAL OF PARTICIPANTS**

### **Recruitment**

The trial setting is in secondary care at NIHR Clinical Research Network sites with dedicated Research Coordinators who will facilitate recruitment and follow-up to discharge or death. Adoption of the trial from the NIHR Clinical Research Network has been sought.

Participants will be recruited from the hyperacute stroke unit or emergency department. The initial approach will be from a member of the patient's usual care team, which may include Investigators and Research Coordinators.

The investigator or their nominee, e.g., from the research team or a member of the participant's usual care team, will inform the participant or their nominated representative (other individual or other body with appropriate jurisdiction), of all aspects pertaining to participation in the study.

If needed, the usual hospital interpreter and translator services will be available to assist with discussion of the trial, the participant information sheets, and consent forms, but the consent forms and information sheets will not be available printed in other languages.

In view of the narrow time window for enrolment and treatment (2 hours), to ensure thrombolysis is not delayed, and the known safety of the intervention beyond 2 hours after stroke onset; verbal consent will be taken from the participants themselves if they have capacity, or proxy consent from a relative/friend where the participant does not have capacity. In participants who lack capacity and have no relatives present a patch may need to be applied in order to prevent delay in performing CT scan /thrombolysis. The trial will use emergency waiver of consent in accordance with statutory instrument 2006, No. 2984, regulation 2, where participants lack capacity to consent for themselves, all verbal consent will be documented in the medical notes.

### **Assessment of capacity**

The investigator will tell the patient that:

- they have had a suspected stroke
- they have higher than ideal blood pressure that needs to be lowered
- they can be in a trial where they will have patches placed on their back for 2 days which will either contain medicine that will lower their blood pressure, or will not contain the medicine

They will then ask the patient 3 questions to assess their capacity (diagnosis stroke, problem–blood pressure needs lowering, treatment patch). If the patient is able to answer the three questions correctly, capacity is assumed

1. If patient has capacity, they may give verbal consent.
2. If the patient does not have capacity, the investigator will explain the trial to a relative/friend if they are immediately available. The relative/friend who is able to represent patients' views and wishes may then give verbal proxy consent, which will be documented in

the participants medical notes.

Written consent will be obtained after treatment for hospital and community-based follow-up. If the participant has capacity, they will be asked to read and sign the short pictorial combined information sheet and consent form; if they lack capacity a relative/friend will be asked to read and sign the short pictorial combined relative information sheet and consent form.

It will be explained to the potential participant that entry into the trial is entirely voluntary and that their treatment and care will not be affected by their decision. It will also be explained that they can withdraw at any time. In the event of their withdrawal, it will be explained that their data collected so far cannot be erased and we will seek consent to use the data in the final analyses where appropriate.

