## TRIAL / STUDY BACKGROUND INFORMATION AND RATIONALE

**Stroke:** Is common (life-time risk 1/5-6) and devastating (death 25%, dependency 40% at 1 year). Acute treatment is limited to alteplase, mechanical thrombectomy, aspirin, hemispherectomy and stroke unit care. Anticoagulation is ineffective, neuroprotection unproven, and there is no widely-agreed treatment for intracerebral haemorrhage (ICH) although lowering blood pressure (BP) may be beneficial. Developing new interventions in hospitals has failed, in part, due to delayed treatment beyond the 'golden' hour after stroke. The management of physiological disequilibrium - BP, oxygen, glucose, cerebral oedema - remains unclear, and it is reasonable to hypothesise that their treatment, if warranted, should start rapidly after stroke onset.

**High BP:** Is common (80%) in patients with acute IS and ICH, and is associated independently with increased early recurrence and late death or dependency. Whether lowering BP improves outcome through reducing expansion and recurrence, or worsens it through reducing cerebral blood flow (due to dysfunctional autoregulation) remains unclear, in part because most trials started treatment several hours after onset. When assessing functional outcome, trial results have varied from a strong positive trend (INTERACT-2: SBP 14 mmHg lower with intensive treatment in ICH) through neutral effect (IMAGES: BP 4/3 mmHg lower with intravenous magnesium in mixed IS/ICH; CATIS: systolic BP 9 mmHg lower with intensive treatment in IS; ENCHANTED-BP SBP 5.5 mmHg lower with intensive BP-lowering in IS) to strong negative trend (BEST: oral propranolol or atenolol in mixed IS/ICH; INWEST: intravenous nimodipine in IS; SCAST: BP 5/2 mmHg lower with oral candesartan in mixed IS/ICH). Meta-analysis, and meta-regression of trial outcomes versus BP change, have not identified benefit.

**Nitric oxide (NO) and donors such as glyceryl trinitrate (GTN):** Are candidate treatments for acute stroke and multiple mechanisms exist by which they might be effective; taken together, these actions may 'buy time' for the brain, protect it and prime patients for arterial reperfusion therapies:

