- GTN is safe in patients with severe carotid stenosis.

Further, the effect of GTN on functional outcome appears to be time-dependent when administered after stroke:

[figure not shown]
- <2.0 hours: No effect; indeed, GTN may cause harm in ICH in this ultra-acute period (interpretation from RIGHT-2 )
- 2.5 to 5.5 hours: May improve functional outcome (interpretation from ENOS-early  and meta-analysis, Figures 1 , 2).
- >6 hours: No effect (interpretation from GTN 1/2/3 and ENOS and an individual patient data meta-analysis ).

(The positive effect of GTN on functional outcome in the phase II RIGHT trial is ignored here because it was small.)

**Figure 1. Meta-analysis of GTN versus no GTN on end of trial functional outcome in patients treated within 6 hours of stroke onset (from )**

**Figure 2. Meta-analysis of GTN versus no GTN on end of trial death in patients treated within 6 hours of stroke onset (from )**

In summary, GTN has been associated with beneficial effects on function and other clinical outcomes in hospitalised patients treated up to 6 hours after ictus. However, benefit was not seen in patients treated prior to hospital admission and there was weak evidence that ultra-acute treatment within 2 hours was associated with harm. As a result, ENOS-2 will assess, in a novel design, the feasibility of recruiting patients between 3 and 5 hours after ictus; if feasible, a larger safety and efficacy trial will be performed in this group of patients.

ENOS-2 will assess the feasibility, safety, and efficacy of hospital-delivered GTN when administered hyper-acutely after stroke. Five of the six GTN trials had a lower limit for systolic blood pressure of  $\geq 100$  mmHg,  $>120$  mmHg or  $\geq 140$  mmHg, the first study had no lower limit. Since several potential mechanisms by which GTN might work are BP-independent, ENOS-2 will follow the RIGHT-2 protocol and include patients with high-normal BP as well as high BP, with a lower limit set to  $\geq 120$  mmHg. This has the advantage that the results will apply to a wider population of stroke patients and include more patients with severe stroke (some of whom have SBP  $<140$  mmHg).

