## **Eligibility criteria**

### **Inclusion criteria**

- Adults ( $\geq 18$  years)
- Presentation compatible with hyperacute stroke syndrome
- One or more of the following symptoms present at time of enrolment: Dysphasia, neglect (NIHSS 1-2), hemianopia (NIHSS 1-3), or limb weakness (NIHSS on affected arm and/or leg 1-4)
- Treatment can be commenced between 3 and 5 hours from onset of symptoms (for patients with wake-up stroke, treatment no more than 5 hours after patient awakens)
- Systolic BP  $\geq 120$  mmHg
- If a CT/MR scan has already been performed, then it shows acute intracerebral haemorrhage or ischaemic stroke, or is normal. (If a CT scan has not been performed then it should be performed as soon as possible after treatment)
- For participants who lack capacity to consent for themselves and have no relative/friend available: Waiver of consent for treatment to ensure GTN given in 3-5-hour time-window (and thrombolysis not delayed if ischaemic stroke)

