### ***Consent for treatment where participants lack capacity***

Participants who lack capacity but have a relative/friend present will be asked to provide verbal consent followed by written consent or proxy written consent after treatment for hospital and community-based follow-up. Ability to give consent will be determined by the participant's attending stroke physician or investigator as previously described:

- **Proxy consent.** Participants who regain capacity will be approached to give consent for further follow up, or to withdraw from the trial. Participants who die after treatment and before consent will have their data used without proxy consent since this avoids unnecessary stress to grieving relatives.

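### The capacity script states as fact, whatever the reading, that the patient's blood pressure must come down, which the protocol's own rationale and entry limit do not support

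*Protocol*

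**What the plan says.** The protocol section Assessment of capacity sets out what the investigator tells the patient: that a stroke is suspected, that "they have higher than ideal blood pressure that needs to be lowered", and that the trial uses patches which either do or do not contain a medicine that lowers blood pressure. Then: "They will then ask the patient 3 questions to assess their capacity". The three items are the diagnosis, the blood pressure problem and the patch treatment. The pass rule is: "If the patient is able to answer the three questions correctly, capacity is assumed".

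The section on participants who lack capacity points back to this procedure: "Ability to give consent will be determined by the participant's attending stroke physician or investigator as previously described". The next steps are also given. "If the patient does not have capacity, the investigator will explain the trial to a relative/friend if they are immediately available". The Inclusion criteria add a route for when nobody is available: "For participants who lack capacity to consent for themselves and have no relative/friend available: Waiver of consent for treatment".

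Elsewhere, the Background summarises the evidence on lowering blood pressure in acute stroke: "Meta-analysis, and meta-regression of trial outcomes versus BP change, have not identified benefit". Its closing paragraph says that the trial will "include patients with high-normal BP as well as high BP, with a lower limit set to" 120 mmHg systolic, and gives as a reason that several possible mechanisms do not depend on blood pressure. The Eligibility criteria carry the same limit and set no upper one.

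**The concern.** The script turns an open question into a premise. A patient deciding within a two-hour treatment window hears that something is wrong and must be corrected, and then that one patch contains the correcting medicine and the other does not. A listener could take the sham arm to mean going without something needed. The protocol's rationale does not say that.

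The same premise then serves as a test item. A capacity question should have an answer that is true for everyone asked. A patient who understands the situation well, knows that the reading is close to normal and says so has given the answer that the protocol does not accept. Two things are at stake: the soundness of the only consent taken before treatment, and the risk that someone able to decide is treated as unable to.

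**Working it through.** The plan states no figure on this point, so the check compares passages.

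1. **Is the statement conditional on the reading?** No. Assessment of capacity attaches no threshold to it, and no other section limits it to patients with hypertension.

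2. **Who can hear it?** Anyone eligible whose capacity is assessed this way. Entry needs a systolic pressure of at least 120 mmHg, so a patient at 125 mmHg qualifies. The Background calls part of this range high-normal and includes it on purpose. Such a pressure may still be described as above ideal. It does not follow that it has to be reduced.

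3. **Does the rationale support a need to lower it?** The Background leaves open whether lowering pressure helps, by limiting expansion and recurrence, or harms, by reducing cerebral blood flow, and it reports no benefit identified on pooling. Protocol Table 2 also points in different directions for GTN itself (modified Rankin Scale, odds ratio below 1 favouring GTN):
   - ENOS overall: 1.01 (0.91 to 1.13)
   - ENOS patients randomised within 6 hours: 0.53 (0.34 to 0.82)
   - RIGHT-2: 1.25 (0.97 to 1.60)

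   These figures justify a trial. They do not justify telling a patient that the need is established.

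4. **Is it corrected before the patch is applied?** Not for a patient with capacity. Assessment of capacity and the section Patient able to provide consent place the written form, with its pictorial information, after treatment.

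5. **What follows if the second item is not answered as expected?** The only stated criterion is three correct answers, and the later section refers back to it. A patient who does not meet it has no other stated way to be judged capable. The routes then described are a relative or friend or, if none is available, the waiver. The waiver is reserved for people who lack capacity, so a capable patient sent there would fall outside its own condition.

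6. **How often?** The documents give no systolic distribution for this trial, no expected pass rate on the three items and no data on how patients respond to the script. No rate can be derived.

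**The case against.** The strongest reply is that the questions come straight after the patient has been told the answers, so they test understanding and recall rather than agreement. The pass rule is also a sufficient condition: the text never says that a wrong answer proves incapacity, and the decision rests with the attending stroke physician or investigator. This stands in part. It makes misclassification a possibility rather than a stated consequence. It does not supply another criterion, and it does not make the premise true.

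A second reply is that the script is not the whole disclosure. The Recruitment section requires the participant to be informed about every aspect of taking part, and patients are told that entry is voluntary. That is correct, but a general duty to inform does not withdraw a specific statement that the investigator is instructed to make. The Background also allows that lowering pressure may be beneficial in intracerebral haemorrhage. That is a possibility, in a planned 20 of 120 participants.

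A reader might infer more than the documents support:

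- **A count of affected patients.** The Background puts high blood pressure at 80% in acute stroke, so 120 × (1 − 0.80) = 24 looks available. High is not defined there, and patients below 120 mmHg are excluded. If a share x of all patients is excluded for that reason, the enrolled share without high pressure is (0.20 − x)/(1 − x). Assuming x = 5% or 10% gives 15.8% or 11.1%, about 19 or 13 of 120. So 24 is a ceiling under the 80% figure, and it counts neither false statements nor misclassified patients.
- **More open-label blood pressure lowering on sham.** Patients and relatives are masked and hear the same words in both arms. The script gives them no reason to ask for more treatment on sham.
- **Damage to consent-route data.** Consent route is not a listed endpoint, nor a feasibility measure in SAP Table 2.
- **Relatives hearing the same claim.** The wording is prescribed for the patient only. For relatives the investigator simply explains the trial.

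**Conclusion.** The conflict is real and narrow. Assessment of capacity presents as settled a question that the Background leaves open, and it does so to patients whom the trial enrols with high-normal pressure. The difficulty lies in the claim that the pressure has to be lowered, not in calling it above ideal.

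The statement reaches every patient whose capacity is assessed with this script. The routing of a capable patient to proxy consent or the waiver is an inference. It assumes that sites apply the three-item rule as the working test, because no other is given, and its frequency is unknown. No endpoint, sample size or planned analysis changes. The reason to act is that the only pre-treatment consent from a patient with capacity should not follow a statement that the protocol itself does not support, and the correction is small.

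**What to change.** Reconcile Assessment of capacity with the Background and the Inclusion criteria:

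- Remove from the second statement the claim that the pressure has to be lowered. Say instead that the trial tests a patch that lowers blood pressure, and that it is not yet known whether this improves recovery after stroke.
- Replace the second capacity item with a recall item that is just as simple and is true for every eligible patient, for example that this is a research study testing a patch.
- Align the information sheet if it repeats the present wording.

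Two alternatives are best avoided. Wording that says the patch may help, harm or make no difference would sit badly with the Recruitment and Informed consent sections, which describe GTN as safe beyond about 2 to 2.5 hours. An item testing the grasp of uncertainty is more abstract than one testing recall. It could raise failures among patients with dysphasia and send more of them to proxy consent or the waiver.

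Treatment, eligibility and blood pressure management stay as they are. The cost is a two-line protocol amendment, ethics review of the wording and brief site retraining.
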